2.2.3 Concomitant therapy

The start/stop dates recorded in the electronic case report form (eCRF) will be used to identify when a concomitant medication or a significant non-drug therapy was taken during the study.

Concomitant medications and significant non-drug therapies after the start of the study treatment will be listed and summarized by ATC class and standardized medication term for the Safety Set. These summaries will include medications starting on or after the start of study treatment or medications starting prior to the start of study treatment and continuing after the start of study treatment. Any prior medications and significant non-drug therapies starting and ending prior to the start of study treatment will be listed. These analyses will be based on Safety Set.

Results of concomitant medications and significant non-drugs medications will be listed. Records after 30 days of end of treatment period will be flagged.

Any missing start date will be queried for resolution. For any unsolved missing start dates, the following rules in the following order will be applied to decide if a concomitant medication or a significant non-drug therapy was taken after the start of the study treatment and to decide if the data should be included in the summary table. Originally collected start date will be listed in listings.

- If the date is completely missing, the Day 1 date will be used as the missing start date.
- If only the day is missing, and the last day of the month is prior to Study Day 1, the concomitant medication will be then considered as starting prior to Day 1.
- If only the day is missing, and the 1st day of the month is after the 1st dosing date on Day 1, the concomitant medication will then be considered as starting after Day 1.
- If only the day is missing, and the month is equal to the month of the 1st dosing date on Day 1, Study Day 2 will be used as the missing day.
- If both the month and day are missing, and the last day of the year is prior to Study Day 1, the concomitant medication will then be considered as starting prior to Day 1.

No rule will be applied to any missing stop date. If *Start/Stop* will be the start/stop date of a concomitant medication, *Date1* will be the date of first INC dose, the concomitant medication will then be allocated to 1 or more summary groups according to the following algorithm as shown in [Table 2-1](#).

Table 2-1 Allocation of concomitant medications

If	Prior Medication	Treatment Phase
Stop≤Date1	X	
Start≤Date1 and Stop=missing and ongoing	X	X
Start≤Date1≤Stop	X	X
Start>Date1		X

2.2.4 Prior medications to treat MF

Prior medications to treat MF will be summarized. The information will include drug name, start and stop dates, best response to therapy, and reasons for discontinuations. This information will be summarized by World Health Organization (WHO) drug class (ATC class) and WHO drug term (the most recent version available), and will be listed by subject, age, sex, MF type, MF therapy name, start and stop dates, and best response.

2.2.5 Compliance

Compliance to the study protocol will be assessed by reporting the number and type of CSR reportable protocol deviations. These will be identified in the VAP document for Protocol Deviation prior to database lock and will be listed and summarized. Compliance to study drug, for the period from Study Day 1 to end of first cycle, i.e. RDI for the first cycle of treatment will be summarized by categories of < 83.3% vs. ≥ 83.3% and will be reported by dose level.

2.3 Safety evaluation

For all safety analyses, the Safety Set will be used, except for summaries of DLTs, which will be presented for the DDS. All listings will be presented by dose levels and all tables will be presented by groups of dose levels in the Safety Set.

The overall observation period will be divided into three mutually exclusive segments:

1. pre-treatment period: from day of patient's informed consent to the day before first dose of study medication
2. on-treatment period: from day of first dose of study medication to 30 days after last dose of study medication
3. post-treatment period: starting at day 31 after last dose of study medication.

2.3.1 Bayesian logistic regression model

The primary objective of the study is to determine the maximum safe starting dose (MSSD) of INC424 given orally, twice-a-day, in a 28-day cycle to patients with myelofibrosis who have baseline platelet counts belonging to 1 of 2 strata: (1) [75 - 100 x 10⁹ / L) or (2) [50 - 75 x 10⁹ / L).

The corresponding primary analysis method is an adaptive Bayesian logistic regression model guided by escalation with overdose control (EWOC). A prior distribution for the model parameters is derived based on experience with INC424 in adult patients in clinical study [INCB

[18424-251](#)], which was the dose-finding study in patients with myelofibrosis that preceded the pivotal phase III studies [\[INC424A-351\]](#) and [\[INC424A-352\]](#). This prior distribution is then updated after each cohort of patients in each stratum with the DLT data from the current study.

The statistical model for MSSD estimation will be based on a 3-parameter Bayesian logistic regression model. Let $\pi_{(d)}$ be the probability of DLT at total daily dose d (in mg), and let d^* denote a reference dose of INC424. Then the 3-parameter logistic model relating the log-odds for a DLT to the dose and stratum is of the form

$$\text{logit}(\pi_{(d)}) = \log(\alpha) + \beta \log(d/d^*) + \gamma I_{\{\text{pt is in stratum 2}\}},$$

where $\text{logit}(\pi_{(d)}) = \log_e(\pi_{(d)}/(1-\pi_{(d)}))$, $\alpha, \beta > 0$, and $-\infty < \gamma < \infty$. Doses are rescaled as d/d^* , and as a consequence α is equal to the odds of the probability of DLT at d^* for a patient in stratum 1. If a patient is from stratum 2, the indicator $I_{\{\text{pt is in stratum 2}\}}$ takes the value 1, otherwise it takes the value zero. Therefore, γ may be interpreted as the log-odds ratio for the probability of DLT between patients from stratum 2 to patients from stratum 1.

After each cohort of patients is completed within a stratum, the posterior distribution for the model parameters will be obtained by simulation. The posterior distributions of the model parameters are used to derive the posterior distributions for $\pi_{(d)}$. The posterior distributions for $\pi_{(d)}$ will be summarized by the following three intervals

- [0,16%) under-dosing
- [16%,33%) targeted toxicity
- [33%,100%) excessive toxicity

Following the principle of dose-escalation with overdose control (EWOC), after each cohort of patients the recommended dose is the one with the highest posterior probability of DLT in the target interval [16%, 33%) among the doses fulfilling the overdose criteria, namely that there is less than 25% chance that the true rate of DLT falls in the excessive toxicity interval. The dose recommended by the adaptive BLRM for each stratum may be regarded as information to be integrated with a clinical assessment of the toxicity profiles observed thus far in determining the next dose to be investigated.

Once the MSSD is established for both strata the BLRM will be updated with DLT information and a table with posterior probabilities of DLT for different doses by stratum will be included in the study report.

Specific safety event categories (SEC) include groups of reported adverse events of high interest as outlined in the product case retrieval sheet. The version of the most up to date document used for the clinical study report will be provided in tables footnotes.

For each specified SEC, number and percentage of patients with at least one event part of the SEC will be reported.

One summary table will be produced for AE to summarize the number (%) of patient from Safety Set:

- who died.
- who died during study treatment and within 30 days after discontinuation of study treatment.
- Who died after 30 days from treatment discontinuation
- reporting AEs regardless of relationship to study treatment.
- reporting AEs with suspected relationship to study treatment.
- reporting SAEs regardless of relationship to study treatment.
- reporting SAEs with suspected relationship to study treatment.

- reporting AEs of CTC grade 3-4 regardless of relationship to study treatment.
- who discontinued from study due to AEs.
- AEs requiring study drug dose adjustment or interruption
- reporting AEs of specific safety event categories. The list of categories will be based on the latest version of case retrieval sheet.

The following summaries will be produced for patients in the Safety Set with number (%) of patients:

- reporting AEs, regardless of relationship to study drug, by system organ class and preferred term.
- reporting AEs, regardless of relationship to study drug, by preferred term.
- reporting AEs, for patients who died, by system organ class and preferred term.
- reporting SAEs, regardless of relationship to study drug, by system organ class and preferred term.
- reporting AEs leading to discontinuation, regardless of relationship to study drug, by system organ class and preferred term.
- reporting AEs requiring dose adjustment or study-drug interruption, regardless of relationship to study drug, by system organ class and preferred term.
- reporting specific safety event categories (SEC), regardless of relationship to study drug, by SEC category.
- reporting AEs, with suspected relationship to study drug, by system organ class and preferred term.
- reporting SAEs, with suspected relationship to study drug, by system organ class and preferred term.
- reporting AEs leading to discontinuation, with suspected relationship to study drug, by system organ class and preferred term.
- reporting AEs requiring dose adjustment or study-drug interruption, with suspected relationship to study drug, by system organ class and preferred term.
- reporting AEs, but not SAEs, regardless of relationship to study drug, by system organ class and preferred term .

Additional outputs to cover RMP commitments may be added in this analysis.

2.3.3 Laboratory abnormalities

For laboratory tests covered by the Common Terminology Criteria for Adverse Events (CTCAE) version 4.03 ([NCI 2009](#)). A grade 0 will be assigned for all non-missing values not graded as 1 or higher. Grade 5 will not be used. All lab values occurring between the treatment start date and 30 days after the end of the study treatment will be taken into account.

The following by-strata summaries will be generated separately for hematology, coagulation and biochemistry laboratory tests:

- frequency table for newly occurring or worsened on-treatment abnormalities
- shift tables using CTCAE grades to compare baseline to the worst on-treatment value

- for laboratory tests where CTCAE grades are not defined, shift tables using the low/normal/high/(low and high) classification to compare baseline to the worst on-treatment value.
- listing of all laboratory data with values flagged to show the corresponding CTCAE grades and the classifications relative to the laboratory normal ranges.

A summary and a plot will be produced for hemoglobin level and platelet count over time by visit and stratum.

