2.1.3 Treatments

During the study all patients will receive INC424 tablets. INC424 tablets will be the only investigational drug in this study.

The following notation will be used for the dose levels by stratum:

Daily dose regimens Morning dose + evening dose	Dose levels	Dose levels for stratum 1	Dose levels for stratum 2	Reporting for stratum 1	Reporting for stratum 2
5mg AM + 5mg PM	1	S1D1	S2D1	Group 1	Group 1
5mg AM + 10mg PM	2	S1D2	S2D2	Group 1	Group 1
10mg AM + 10mg PM	3	S1D3	S2D3	Group 2	Group 2
10mg AM + 15mg PM	4	S1D4	S2D4	Group 3	Group 3
15mg AM + 15mg PM	5	S1D5	S2D5	Group 3	Group 3

Baseline for efficacy and safety assessments is defined as last assessment prior to or on the first INC dose date unless there is a separate definition provided [REDACTED].

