2.3.4 Other safety data

Vital signs

The following thresholds will be used for the notable abnormal vital signs

Table 3-2 Criteria for clinically notable vital sign abnormalities

Parameter	High Threshold	Low Threshold
Systolic Blood Pressure	> 160 mm Hg	< 85 mm Hg
Diastolic Blood Pressure	> 95 mm Hg	< 50 mm Hg
Pulse Rate	> 100 bpm	< 50 bpm
Respiratory Rate	> 24 per minute	< 8 per minute
Body temperature	>38°C	<35.5°C

bpm = beats per minute

The number and percent of subjects with notably abnormal vital signs, defined as the absolute value being out of the above defined range, will be summarized by treatment group.

A summary table will be produced for incidence of notably abnormal vital sign abnormalities, i.e. shift table from baseline to worst on-treatment result.

A summary table will be produced with descriptive statistics at baseline, worst post-baseline and change from baseline to the worst post-baseline.

ECG

The following analysis will be done for ECG data

- Shift table baseline to worst on-treatment result for overall assessments
- Listing of ECG evaluations for all patients will also present any abnormality

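### The Day 1 record counts both as baseline and as on-treatment, so the baseline-to-worst shift tables hide improvement, show patients with no post-dose value as unchanged, and can produce false '(low and high)' results

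*SAP*

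**What the plan says.** Four rules in the SAP meet on the date of first dose.

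- **Baseline (SAP 2.1.3):** "Baseline for efficacy and safety assessments is defined as last assessment prior to or on the first INC dose date". The sentence goes on to allow a separate definition, part of which is blacked out. No separate definition is visible for laboratory, vital-sign or ECG data.
- **Periods (SAP 2.3, matched by protocol 9.5.2.1):** "pre-treatment period: from day of patient's informed consent to the day before first dose of study medication", then "on-treatment period: from day of first dose of study medication to 30 days after last dose of study medication".
- **Laboratory values used (SAP 2.3.3):** "All lab values occurring between the treatment start date and 30 days after the end of the study treatment will be taken into account".
- **Tables:** for graded tests, "shift tables using CTCAE grades to compare baseline to the worst on-treatment value"; for ungraded tests, "shift tables using the low/normal/high/(low and high) classification to compare baseline to the worst on-treatment value"; also a "frequency table for newly occurring or worsened on-treatment abnormalities". SAP 2.3.4 plans for ECG a "Shift table baseline to worst on-treatment result for overall assessments", and a similar shift table for vital signs. Only the vital-sign descriptive table refers to the worst post-baseline value.

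Protocol Table 6-1 schedules hematology, chemistry, coagulation, vital signs and ECG on Day 1. Protocol 6.2.2.7.1 confirms the ECG.

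**The concern.** All of these rules work on dates, without clock times. A Day 1 record cannot be pre-treatment, because that period ends the day before. It is the baseline, or at least a candidate for it, and it is also the first on-treatment value. The worst on-treatment value can then never be better than baseline, and it exists even for a patient who has no later measurement.

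What is at stake is how the safety shift tables read. Recovery from an abnormal baseline cannot be seen, and absent follow-up looks like stability. Abnormal baselines are to be expected here: the entry criteria admit hemoglobin below 10 g/dL, INR and PTT up to 1.5 times the upper limit of normal, and ALT up to 2.5 times.

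**Working it through.** The plan gives no figure on this point to reproduce. The check applies the rules as written to every possible outcome, then repeats it with the baseline record excluded.

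**Graded tests.** Let b be the Day 1 grade (0 to 4, one scale per test) and w the worst grade after Day 1 (0 to 4, or none). That makes 5 × 6 = 30 combinations.

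- As written: worst on-treatment = max(b, w), or b if there is no w.
- Baseline record excluded: worst on-treatment = w, or missing if there is no w.

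The combinations divide into 10 with w > b, 5 with w = b, 10 with w < b and 5 with no w.

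| Rule | Worse | Same | Better | Missing |
|---|---|---|---|---|
| As written | 10 | 5 + 10 + 5 = 20 | 0 | 0 |
| Baseline record excluded | 10 | 5 | 10 | 5 |

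All 10 improving combinations and all 5 without a later value move onto the diagonal. Since max(b, w) > b exactly when w > b, the worsening cells and the number of newly occurring or worsened abnormalities are identical under both rules.

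**ECG, taken as normal or abnormal.** There are 2 × 3 = 6 combinations. As written they give 1 worse and 5 same. With the baseline record excluded they give 1 worse, 2 same, 1 better and 2 missing.

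**Ungraded tests.** Three baseline classes (low, normal, high) against five later outcomes (normal, low, high, low and high, none) give 15 combinations. The two rules differ in 7:

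- low or high on Day 1 and normal afterwards is shown as unchanged (2);
- low then high, or high then low, is shown as low and high on treatment (2);
- no later value is shown as unchanged (3).

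**Where a later value could be absent.** In Table 6-1, hematology and chemistry are repeated on Day 15. Coagulation and ECG are first repeated on Day 29. Table 6-3 adds end-of-treatment hematology and chemistry, and Table 6-2 adds an end-of-treatment ECG if it falls before Day 168. No end-of-treatment coagulation test is visible, although Table 6-3 has a redacted row. A patient who stops before Day 29 is thus most likely to lack a post-dose value for coagulation.

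**Weight of one patient.** About 20 patients are planned at the Stratum 1 dose of 10 mg BID. One misplaced patient in a group of that size moves a percentage by 1/20 = 5 points.

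**The case against.** The strongest reply is that worst-value shift tables exist to show deterioration, and deterioration is reported correctly. That is true for the graded tables. Other planned outputs also show what these tables hide: flagged listings of all laboratory data, hemoglobin and platelet summaries by visit, ECG listings for all patients, and vital-sign change to the worst post-baseline value. A programmer may exclude the baseline record as a matter of habit, and the Master Analysis Plan named in the protocol's abbreviation list, which is not available here, may say so. But then the outputs would rest on a rule the SAP does not state, and two programmers following the text could produce different tables.

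A reader might infer more than the documents support:

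- **That pre-dose abnormalities are generally attributed to treatment.** They are not. A high-to-high patient sits on the diagonal and is not counted as new or worsened. The inference holds only for ungraded tests that are abnormal in opposite directions.
- **That with k later visits the baseline is wrongly the worst value with probability 1/(k+1), for example 25% for ECG at k = 3.** That is the chance that one of k+1 exchangeable continuous values is the extreme, not the chance of a wrong category. For a two-level result with independent visits, each abnormal with probability p, the error needs an abnormal baseline and k normal visits: p(1−p)^k. At k = 3 the maximum, at p = 0.25, is 0.25 × 0.75³ = 10.5%; at p = 0.1 it is 0.1 × 0.9³ = 7.3%. The value of k is also larger than the core schedule suggests for hematology and chemistry, because the SAP pools core and extension data. Platelets are not exchangeable over time either: the protocol reports that in the earlier study they fell mainly in the first 4 weeks. No such percentage should be quoted as the size of this problem.
- **That no patient at all can show improvement.** If the Day 1 value is missing, baseline falls back to Screening, which lies outside the on-treatment window, and improvement can appear.
- **That the main results are affected.** The primary endpoint is DLT, and the secondary safety endpoint is built on adverse events. Neither is derived from these tables.

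**Conclusion.** The point holds as a fault in a stated derivation rule. Followed literally, the SAP places every improving patient who has a Day 1 value, and every patient with a Day 1 value but nothing later, in a no-change cell. It also creates false low-and-high results for some ungraded tests. The effect is confined to the shift tables and to who is counted in them. Worsening shifts in graded tables, the numerator of the newly occurring or worsened table, and the DLT and MSSD analysis stand.

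The number of patients affected cannot be derived from the documents.

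Assumptions: Day 1 values are available, as Table 6-1 schedules (this is the post-Amendment 4 schedule, and many patients were enrolled before it); and the redacted exception in SAP 2.1.3 does not cover these data. The documents do not say outright that Day 1 samples precede dosing. Use of the Day 1 platelet count for eligibility and stratum, and dosing in the clinic that day, make it likely. The overlap does not depend on it, because the rules use dates only.

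**What to change.** In SAP 2.3.3 and 2.3.4, define the worst on-treatment value for all shift tables (laboratory, vital signs, ECG) as the worst value recorded after the baseline record and up to 30 days after last dose, with the record used as baseline excluded. Show patients with no post-baseline value in a missing column and state the denominator. This matches the post-baseline wording that SAP 2.3.4 already uses for the vital-sign descriptive table. The on-treatment definition for adverse events can stay: SAP 2.3.2 already has its own Day 1 and Day 2 rules for onset.

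Cost: one sentence in the SAP, one filter in the shift-table program and one added table column. No new data are needed.

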2.3.4 Other safety data

Vital signs

The following thresholds will be used for the notable abnormal vital signs

Table 3-2 Criteria for clinically notable vital sign abnormalities

Parameter	High Threshold	Low Threshold
Systolic Blood Pressure	> 160 mm Hg	< 85 mm Hg
Diastolic Blood Pressure	> 95 mm Hg	< 50 mm Hg
Pulse Rate	> 100 bpm	< 50 bpm
Respiratory Rate	> 24 per minute	< 8 per minute
Body temperature	>38°C	<35.5°C

bpm = beats per minute

The number and percent of subjects with notably abnormal vital signs, defined as the absolute value being out of the above defined range, will be summarized by treatment group.

A summary table will be produced for incidence of notably abnormal vital sign abnormalities, i.e. shift table from baseline to worst on-treatment result.

A summary table will be produced with descriptive statistics at baseline, worst post-baseline and change from baseline to the worst post-baseline.

ECG

The following analysis will be done for ECG data

- Shift table baseline to worst on-treatment result for overall assessments
- Listing of ECG evaluations for all patients will also present any abnormality

2.4 Pharmacokinetic evaluations (PK, PK/PD)

The pharmacokinetics will be evaluated by population pharmacokinetic modeling methods in a separate report. The analysis plan of this report and conduct of the analysis will be done by Incyte.

2.4.1 Pharmacokinetic-Pharmacodynamic data analysis

Relationships between the pharmacokinetic model predicted concentration/PK parameters and PD and safety/efficacy parameters were planned. All these as well as cytokines (if analysis

permitted) and depending on the quality of data available, may be reported in the a separate report Efficacy evaluation

Efficacy is a secondary endpoint in this study.

Change in spleen length below left costal margin

Spleen measurements by palpation will be obtained with a primary emphasis on the change in measurements from baseline to Week 24. Descriptive statistics will be provided for the spleen length and percent change from baseline over time. The percentage of patients with at least a 50% reduction in spleen length at any time point prior to cut off date (including both core and extension phases) as well as at least a 50% reduction in spleen length at Week 24 will be summarized with 95% confidence intervals.

Data will be summarized for the set of patients from the FAS who have a valid corresponding baseline assessment.

The percentage change in spleen length is defined as:

[figure not shown]
% Change = $(\text{Post-baseline spleen length} - \text{Baseline spleen length}) \times 100 / \text{Baseline spleen length}$.

A waterfall plot will be produced for best response in spleen length by stratum. Best response is defined as the minimum value in non-missing percent change from baseline.

Spleen length measurement with absolute and percent change from baseline will be summarized by time and by stratum.

For Interim Analysis, the current protocol time windows as specified in the latest protocol amendment Tables 6-3, 6-4, 6-5, 6-6 will be used for all visit based assessments.

